5.2.1.4 We will first treat 6 patients at dose level -1 in the lead-in phase. If DLT occurs in $\geq 2/6$ patients, this dose level would exceed the MTD, and 6 patients will be treated at the next lower dose level (i.e. dose level -2). If DLT is observed in the first 28 days of treatment in 0 or 1/6 at dose level -1, then dose level 0 will be evaluated. The dose adjustment (Table 1) will continue in cohorts of 6 until we reach a dose level at which $< 2/6$ patients experience a DLT in the first 28 days. The dose level at which 0-1/6 patients experience a DLT in the first 28 days of treatment will be the MTD and will be used to treat an additional 34 patients in the phase II portion of the study. If $\geq 2/6$ patients experience DLT at dose level -4, the study will be revised to consider additional lower dose levels (based on potential synergistic toxicity).

5.2.1.5 Patients that are removed from study before day 28 for any reason other than toxicity and have not experienced DLT will be replaced.

5.2.2 One cycle of therapy is defined as 28 days. Patients will receive one cycle of therapy every 28 days (+/- 7 days).

5.2.2.1 In the phase II part of the study (once the MTD dose has been defined) cycles may be started early (but not earlier than day 21) for patients with active disease if judged in the best interest of the patient.

For the lead-in cohort, DLT defining period is 28 days. As such, cycle 2 should not be started before 28 days for the patients being treated on the lead-in cohort.

5.2.2.2 Subsequent cycles may be delayed for recovery of toxicity or other medical conditions (e.g. infections). Delays in start of subsequent cycles greater than 8 weeks will be acceptable only for patients who are deriving clinical benefit and after discussion with the principal investigator of potential risk/benefit ratio.

5.2.2.3 In instances where one drug has to be discontinued transiently because of safety, the administration of the other drug may continue as scheduled. If the drug that is held can resume at a later time, no doses will be made up and the administration will follow the originally defined schedule calendar according to the drug that was continued.

5.2.2.4 Subsequent courses of 5-azacytidine and lirilumab may be administered regardless of peripheral blood counts during the first 4 cycles and/or in the presence of residual leukemia.

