5.4 Duration of Therapy

In the absence of treatment delays due to adverse events, treatment may continue until one of the following criteria applies:

1. Clinically significant progressive disease, or
2. Intercurrent illness that prevents further administration of treatment, or
3. Patient request, or
4. General or specific changes in the patient's condition render the patient unacceptable for further treatment in the judgment of the investigator, or
5. Unacceptable toxicity that in the opinion of the investigator makes it unsafe to continue therapy.
 - 5.4.1 It is planned that up to a total of 24 cycles of therapy will be administered for patients deriving benefit from this regimen. Continuation of therapy for patients completing 24 cycles of therapy may be considered on a case-by-case basis after discussion with the principal investigator.
 - 5.4.2. A minimum of 1 full course (defined as the administration of 5-azacytidine for 7 days and one dose of lirilumab) will be required for a patient to be considered as having received an adequate trial to evaluate efficacy. All patients receiving at least one dose of any of the two drugs will be considered evaluable for toxicity.

5.5 Supportive Care:

Supportive care measures including blood products, infection prophylaxis and growth factors will be administered according to institutional and Leukemia Department guidelines.

Supportive care measures including blood products, infection prophylaxis and growth factors will be administered according to institutional and Leukemia Department guidelines.

Management Algorithms for Treatment of Lirilumab Related Adverse Events

Immuno-oncology (I-O) agents are associated with AEs that can differ in severity and duration than AEs caused by other therapeutic classes. Lirilumab is considered an immuno-oncology agent in this protocol. Early recognition and management of AEs associated with immuno-oncology agents such as lirilumab may mitigate severe toxicity. Lirilumab has a known safety profile however, a general principle is that differential diagnoses should be diligently evaluated according to standard medical practice. Non-inflammatory etiologies should be considered and appropriately treated. Corticosteroids are a primary therapy for immuno-oncology drug-related adverse events, and lirilumab is no exception. The oral equivalent of the recommended IV doses may be considered for

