9.1 Discontinuation Criteria for Individual Patients

9.1.1 Patient Withdrawal

Patients may voluntarily withdraw consent to participate in the clinical study at any time and without giving any reason. Their withdrawal will not jeopardize their relationship with their healthcare providers or affect their future care. Patients may also choose to withdraw from study treatment, but agree to remain in the study for follow-up procedures.

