9.1.4 Follow-Up at Treatment Discontinuation or Early Withdrawal

Patients who discontinue treatment for any reason should complete end-of-treatment procedures when possible. End of treatment procedures will include a physical examination, CBC with differential and platelets and a limited chemistry profile (total bilirubin, serum creatinine, SGPT or SGOT). A bone marrow aspiration may be recommended only if non-response or progressive disease cannot be unequivocally diagnosed from peripheral blood. Although treatment will be discontinued at that time, all patients who do not withdraw consent for follow-up, die, or become lost to follow-up, will remain on study for follow-up evaluations. Subject will be followed for toxicity for at least 30 days after the last protocol treatment. The 30-day follow-up visit will be scheduled as a clinic visits for clinical evaluation and physical examinations. If the patient cannot make it to the MDACC clinic for this visit, the required follow up treatment procedures may be done with a local physician and the records forwarded to MDACC. The research nurse will contact the patient by telephone and get a verbal assessment of the patient's condition. The phone conversation will then be documented in the patient's charts.

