11.1 Sample Size

Part a. Lead-in phase

The primary objective of the lead-in phase is to determine the safety of lirilumab in combination with 5-azacytidine in patients with refractory/ relapsed AML. Up to 24 patients will be accrued into lead-in part of the study.

Part b. Phase II

Up to 40 patients (including 6 patients treated at the MTD from the lead-in part) will be recruited for the Phase II part.

The primary objective of the phase II is to determine the efficacy of lirilumab in combination with 5-azacytidine in patients with refractory, relapsed or untreated AML. The efficacy of the combination will be measured by the overall response rate (ORR), defined as CR (complete remission) + CRp (complete remission with incomplete platelet recovery) + CRi (complete remission with incomplete count recovery) + PR (partial response) + marrow clearance of blasts + HI (Hematological improvement) within 3 months of treatment initiation among adult patients with refractory/ relapsed AML. ORR and toxicity will be monitored simultaneously using the Bayesian approach of Thall, Simon, Estey (1995, 1996) and the extension by Thall and Sung (1998).

Once safety of the MTD has been established, any patients still on study at a dose lower than MTD can be dose escalated up to MTD. Patients treated in the lead-in phase at MTD will be included in the phase II portion of the study.

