Monitoring the ORR rate, based on the above assumptions and monitoring conditions is found in Table 5. **For example, accrual will cease if less than 2 patients experience an overall response within 3 months of initiation of therapy in the first 10 patients treated.**

Table 5. Stop accrual if the number with overall response is less than or equal to indicated (i.e., # patients with overall response) among the number of patients evaluated					
# patients evaluated	5	10-15	20-25	30-35	40
# patients with overall response	Never stop with this many patients	0-1	0-2	0-3	Always stop with this many patients

Multic Lean Desktop (version 2.1.0) was used to generate the toxicity and futility stopping boundaries and the OC table (Table 6). In order to utilize the software for the design, a beta (0.3, 1.7) and beta (0.4, 1.6) priors were assumed for the standard treatment response distribution and experimental treatment response prior distribution, respectively. In addition, a 30% toxicity constant rate and beta (0.6, 1.4) priors were assumed for the standard treatment toxicity constant rate and experimental treatment toxicity prior distribution, respectively.

The probability of stopping the study early if the true ORR of the combination treatment was 30% and the true toxicity rate was 30% was 15.1%. Probabilities of stopping early for high true toxicity rates (i.e., 50%) were 84.0% when the true ORR was 30% and 83.6% when true ORR rate was 40%.

Table 6. Operating characteristics for simultaneous monitoring response and toxicity rates for patients treated with combination treatment		
True Toxicity Rate	True ORR	Prob(stop the trial early)
0.10	0.15	0.3001
	0.20	0.1479
	0.25	0.0703
	0.30	0.0328

Table 6. Operating characteristics for simultaneous monitoring response and toxicity rates for patients treated with combination treatment

True Toxicity Rate	True ORR	Prob(stop the trial early)
	0.35	0.0151
	0.40	0.0069
0.20	0.15	0.3101
	0.20	0.1601
	0.25	0.0836
	0.30	0.0466
	0.35	0.0292
	0.40	0.0211
0.30	0.15	0.3859
	0.20	0.2523
	0.25	0.1842
	0.30	0.1514
	0.35	0.1358
	0.40	0.1286
0.40	0.15	0.6194
	0.20	0.5367
	0.20	0.4945
	0.30	0.4741
	0.35	0.4645
	0.40	0.4600
0.50	0.15	0.8841
	0.20	0.8589
	0.25	0.8460
	0.30	0.8398
	0.35	0.8369
	0.40	0.8355

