All patients who received any dose of the study agent will be included in the analysis for efficacy and safety. Demographic/clinical characteristics (including duration of response) and safety data of the patients will be summarized using descriptive statistics such as mean, standard deviation, median and range. For the primary efficacy analysis, we will estimate the ORR for the combination treatment, along with the 95% confidence interval. Patients who drop out of the study before completing all the cycles will be treated as “failures” for the primary analysis. ORR during the study period will also be presented with the 95% confidence interval. The association between ORR and patient’s clinical characteristics will be examined by Wilcoxon’s rank sum test or Fisher’s exact test, as appropriate. Toxicity type, severity and attribution will be summarized for each patient using frequency tables.

The distribution of time-to-event endpoints (DFS and OS) including overall survival and progression free survival will be estimated using the method of Kaplan and Meier. Comparisons of time-to-event endpoints by important subgroups will be made using the log-rank tests. Paired t-tests will be used to determine the immunological and molecular changes in the peripheral blood and bone marrow from baseline to the time of response, and to the time of disease progression. Correlation analysis (such as logistic regression analysis) will be conducted to determine the relationship between induction of hypomethylation / DNA damage and clinical response.

Statistical analysis of biomarker data: Descriptive statistics including plots, mean, median and standard deviations will be used to summarize data. For continuous outcomes, t-test and ANOVA will be used to compare outcome measures across patient characteristics. Dunnett’s and Tukey’s test that properly adjust for multiplicity in multiple tests will be implemented. Pair-wise comparisons will be performed using pre- and post-therapy samples from each patient . The chi-square test or Fisher’s exact test will be used to test the association between two categorical variables such as disease state and performance status. Both univariate and multivariate logistic regressions will be performed to model prognostic factors.

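### The drop-out failure rule for the primary analysis runs to the last treatment cycle, not to the 3-month endpoint window, so a later departure can overwrite a response documented in time

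*Combined protocol and SAP*

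**What the plan says.** **Endpoint.** Section 11.1 (Part b) measures efficacy by the ORR, with response counted "within 3 months of treatment initiation among adult patients with refractory/ relapsed AML". The futility rule in Section 11.2 (Table 5) uses the same window; its worked example counts "overall response within 3 months of initiation of therapy in the first 10 patients treated".

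**Failure rule.** The analysis paragraph of Section 11.2 puts everyone dosed with study agent into the efficacy analysis. It then says "Patients who drop out of the study before completing all the cycles will be treated as" failures for the primary analysis. A second ORR, over the whole study period, is also to be reported.

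**How long the cycles last.** Section 5.4.1: "It is planned that up to a total of 24 cycles of therapy will be administered for patients deriving benefit from this regimen". It adds: "Continuation of therapy for patients completing 24 cycles of therapy may be considered on a case-by-case basis". Section 5.2.2: "One cycle of therapy is defined as 28 days", with a tolerance of 7 days either way.

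**Leaving treatment versus leaving the study.** Section 9.1.1: "Patients may also choose to withdraw from study treatment, but agree to remain in the study for follow-up procedures". Section 9.1.4 says that after treatment stops, "all patients who do not withdraw consent for follow-up, die, or become lost to follow-up, will remain on study". The term drop-out itself is not defined.

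**The concern.** The endpoint is settled at 3 months, but the failure rule keeps acting until the patient has finished a number of cycles that the protocol does not fix. Nothing in the text limits the rule to the window or protects a response already on record. An event well after the window can therefore change a patient's primary outcome from response to failure. Responders are the most exposed, because extended treatment is meant for those deriving benefit.

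At stake is the primary estimate. Section 11.2 calls the regimen worth pursuing if the ORR rises to 30% with acceptable toxicity, so an ORR pushed down by late departures could count against an active regimen. An analyst who applies the sentence literally and one who takes it to mean early leavers without an assessment would also report different primary ORRs from the same data.

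**Working it through.** The point rests on the wording. No figure in the plan uses the failure rule, so there is none to reproduce. The arithmetic below shows only the reach and possible scale.

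**1. Two time limits side by side.**
- Endpoint window (Section 11.1): 3 months = 3 × 30.4375 / 28 = 3.3 cycles of 28 days.
- Failure rule (Section 11.2 with 5.4.1): up to 24 cycles × 28 days = 672 days = 672 / 30.4375 = 22.1 months. With cycles of 21 or 35 days this is 16.6 or 27.6 months.
- Gap at 28-day cycles: 22.1 − 3 = 19.1 months. This is the reach of the planned 24 cycles, not an expected exposure. Many patients will stop sooner, and continuation past 24 cycles would extend it.

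**2. Who counts as a drop-out.** Sections 9.1.1 and 9.1.4 keep a patient who stops treatment on study unless that patient withdraws consent for follow-up, is lost or dies. The narrow reading is therefore withdrawal of consent and loss to follow-up. Death is open: Section 9.1.4 lists it among the reasons for not remaining on study, but Section 11.2 does not say whether it is a drop-out.

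**3. Applying the sentence.** Take a complete remission documented at month 2 and loss to follow-up at month 6, before the last cycle. The definition in Section 11.1 makes this a responder; the sentence in Section 11.2 makes it a failure. Table 5 states no override, so the interim count would keep the patient as a responder.

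**4. Scale (illustrative).** With n = 40 (Section 11.1), one rescored responder moves the ORR by 1/40 = 2.5 points. Let f be the assumed share of 3-month responders rescored, with a true 3-month ORR of 30%. Then:
- expected ORR = 0.30 × (1 − f);
- chance of observing at least 12/40 = binomial upper tail with n = 40 and p = 0.30 × (1 − f);
- chance that at least one of 12 responders is rescored = 1 − (1 − f)^12.

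| f (assumed) | Expected ORR | P(at least 12/40) | P(at least 1 of 12 rescored) |
|---|---|---|---|
| 0 | 30.0% | 0.559 | 0 |
| 2% | 29.4% | 0.526 | 0.215 |
| 5% | 28.5% | 0.476 | 0.460 |
| 10% | 27.0% | 0.392 | 0.718 |
| 20% | 24.0% | 0.236 | 0.931 |

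The plan sets no final cut-off and no test; 12/40 is only the 30% target written as a count.

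**5. If death counts as drop-out.** Larger shares are then conceivable. Section 2.2 reports a median survival of 3.8 months in patients refractory to high-dose-cytarabine induction, and a median response duration of 9 months after salvage. Neither figure describes responders in this trial. With f = 25% or 50%, the expected ORR is 22.5% or 15.0%. As counts with exact 95% intervals:
- 12/40 = 30.0% (16.6% to 46.5%);
- 9/40 = 22.5% (10.8% to 38.5%);
- 6/40 = 15.0% (5.7% to 29.8%).

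**The case against.** The strongest reply is that the sentence is ordinary non-responder imputation. Everyone dosed is analysed, and the rule says how to score those who leave before they can be assessed. Read together with the 3-month definition, it need not override a response already recorded. That may well be the intent, and the documents do not show that anyone meant to overwrite responses. But the sentence sets its limit at the end of the cycles, not at the assessment or the 3-month mark, and no other section supplies the missing limit. The literal reading remains open.

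Three further replies hold in part.
- **The effect is conservative and descriptive.** This stands. Rescoring cannot create a false claim of activity, and the final ORR is an estimate with a confidence interval, not a test. It can still understate activity against the 30% target.
- **Stopping decisions are untouched.** This also stands as the text is written, since Table 5 counts 3-month responses with no override. The price is that interim and final counts may disagree for the same patients.
- **The study-period ORR is a safeguard.** This holds only weakly. The failure rule is worded for the primary analysis, so the second estimate is probably free of it. But that estimate has a different window and cannot replace the 3-month ORR.

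**Conclusion.** The point holds and should be fixed before analysis; it does not undermine the design. The failure rule is not aligned with the 3-month endpoint and, followed literally, lowers the primary ORR by 2.5 points for each in-window responder who later leaves the study, at n = 40. The direction is certain. The size is not, because the documents give no drop-out rate and do not say whether death is a drop-out. Every f in the working is an assumption.

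A reader might infer more than the documents support:
- **That any responder who stops treatment before cycle 24 becomes a failure.** Sections 9.1.1 and 9.1.4 separate stopping treatment from leaving the study, so progression or toxicity that ends treatment is not by itself a drop-out.
- **That responders are typically exposed for 19 months after the window.** That figure assumes all 24 planned cycles at 28 days each; it is not an expected duration.
- **That the loss of ORR can be quantified, or is bound to be small.** Neither follows. The 2% to 20% range is illustrative, and losses could exceed it if death counts.

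**What to change.** Leave the analysis-set sentence in Section 11.2 unchanged, so that the denominator stays as it is, and replace only the failure sentence. Suggested wording:

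> For the primary analysis, a patient who dies, drops out of the study or is not assessed, and who has no response documented within 3 months of treatment initiation, is counted as a failure. A response documented within 3 months counts regardless of later treatment or study discontinuation.

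This still scores early leavers without a documented response as failures, matches the way Table 5 counts responses, and makes the status of later deaths irrelevant to the primary ORR. The cost is two sentences in Section 11.2, with no new data, visits or patients.

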5.2 Schedule

The Investigator is responsible for completing the cohort summary template and submitting to the IND office Medical Monitor for review and approval prior to advancing subjects to the next protocol specified cohort/dose level. A copy of the cohort summary should be placed in the Investigator's Regulatory Binder under "sponsor correspondence". This should be submitted after the first six patients.

5.2.1 Patients will be treated according to the following schedule:

- 5-azacytidine will be administered subcutaneously (SQ) or intravenously (IV) for 7 days of every cycle (Days 1-7) as determined by treating physician. Both SQ and IV forms of administration are FDA approved and considered interchangeable. Patients may start receiving 5-azacytidine by one route and changed to the other at any time as needed based on patient and/or physician preference.
- Lirilumab will be administered as an approximately 60 minute IV infusion on Day 8 (+/-2 days) of each 5-azacytidine cycle. Lirilumab will be administered every cycle with no interruptions unless there are adverse events as described in Section 5.3. The dosing calculations should be based on the body weight. All doses should be rounded to the nearest milligram. There will be no dose reductions (only interruptions when indicated) allowed for lirilumab on this trial.

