7.2 Evaluation During Treatment

- 7.2.1 Physical exam at the start of each cycle (\pm 4 days) and documentation of all concomitant medications.
- 7.2.2 CBC, platelet count, differential once weekly (\pm 4 days) for the first 3 cycles, then every 2-4 weeks (differential can be omitted if WBC is $\leq 0.5 \times 10^9/L$)
- 7.2.3 Creatinine, total bilirubin, ALT once weekly (\pm 4 days) for the first 3 cycles, then every 2-4 weeks.
- 7.2.4 Bone marrow aspiration on day 28 (\pm 7 days), then every 1-3 cycles. Bone marrow tests can be ordered more frequently if mandated by development of peripheral blood counts. No repeat bone marrow is necessary if nonresponse or progressive disease can be unequivocally diagnosed from peripheral blood tests or, in patients with a WBC < 0.3 if the bone marrow test is considered noncontributory by the investigator at any time point.
- 7.2.5 Concomitant medication data will not be collected or entered into the case report form except for concomitant hydroxyurea and cytarabine; however, the subject's medication record will contain a list of concomitant medications.
- 7.2.6 Correlative Studies relating to immunologic response: Tumor tissue, blood samples and bone marrow aspirate will be collected on a separate IRB approved laboratory protocol for immune monitoring as previously published[52-55], under the supervision of the Immunotherapy Platform (MDACC Protocol PA13-0291). Patients will be consented separately on the IRB approved consent for protocol PA 13-0291. Patients may participate in protocol 2014-0862 irrespective of whether they choose to participate on protocol PA 13-0291. In tumor tissues, immunohistochemical studies will be performed to evaluate tumor and immunological cell markers such as CD4 and CD8 T cells. In peripheral blood, we will also evaluate tumor and immune cell populations including but not limited to CD4 and CD8 T cells in pre and post therapy samples.
- 7.2.7

Peripheral blood up to 20 mL (within 24 hours) will be collected under an IRB-approved laboratory protocol for testing of biomarkers at the following time points

- Baseline (prior to 5-azacytidine dose), on day 8 (prior to lirilumab dose), and between days 21 to 28 on cycle 1 (done at MD Anderson).
- In each subsequent cycle blood samples will be obtained on day 1 (prior to 5-azacytidine dose) and day 8 (prior to lirilumab dose) when possible.
- Samples will be collected at progression whenever possible.

Bone Marrow:

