- Bone marrow samples will be collected under an IRB-approved laboratory protocol for testing of biomarkers at baseline, at day 28 (+/-7 days), then every 1-3 cycles, and at progression whenever possible.

All these samples can be obtained +/- 3 days. Missed samples for correlative studies will not constitute protocol deviations. All correlative samples are optional.

- 7.2.8 For patients that remain on study with no significant toxicity for more than 6 months, subsequent evaluations during study may be modified after discussion with the principal investigator. These include a decrease in frequency of bone marrow aspirations to every 6-12 months (or as clinically indicated), correlative studies to every 6-12 months (or suspension of sample collection for correlative studies), other laboratory tests to once every cycle.
- 7.2.9 ALL treatments with lirilumab must be administered at the MDACC outpatient clinic. The first cycles of azacytidine must be administered at the MDACC outpatient clinic. Subsequently, patients will have the option of receiving 5-azacytidine injections or infusions at the MDACC outpatient clinic or local ambulatory treatment center. If the local treatment center cannot accommodate 7 consecutive day administration on Days 1-7 of 5-azacytidine, it is allowable to be administered on a 5+2 (days off) + 2 schedule (For example, Administer Monday through Friday, omit Saturday and Sunday, Resume/Administer Monday and Tuesday). In the event that the 5+2+2 schedule is utilized, the Lirilumab will be administered on Day 10, which is allowable by schedule window or +/- 2 days from Day 8. We do not intend for the subjects to receive lirilumab at an outside physician's office. During the first cycle all the laboratory evaluations will be done at MDACC. Subsequently, the patient may have the laboratory work done at a local clinic and the results reported to the research nurse for the study. The laboratory work done at the local clinic will be forwarded to the patient's attending physician at MDACC or PI of the study, who will sign off on the labs to verify that the results have been reviewed.

Outside Physician Participation During Treatment

1. MDACC Physician communication with the outside physician is required prior to the patient returning to the local physician.
This will be documented in the patient record

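### The only biomarker tests with named time points are timed by the outcome, while the fixed-time cycle 1 samples already scheduled are assigned to no analysis

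*Combined protocol and SAP*

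**What the plan says.** Section 11.2 plans paired t-tests of immunological and molecular change in peripheral blood and "bone marrow from baseline to the time of response, and to the time of disease progression". The same section has two further analyses that bear on these data. One reads "Pair-wise comparisons will be performed using pre- and post-therapy samples from each patient" and gives no time point. The other is a correlation analysis, with logistic regression as the example, relating induction of hypomethylation and DNA damage to clinical response. It does not say when induction is measured.

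Section 7.2.7 schedules cycle 1 blood at fixed times: "Baseline (prior to 5-azacytidine dose), on day 8 (prior to lirilumab dose), and between days 21 to 28 on cycle 1". For later cycles it says "In each subsequent cycle blood samples will be obtained on day 1 (prior to 5-azacytidine dose) and day 8 (prior to lirilumab dose) when possible". Marrow for biomarkers is taken at baseline, at day 28 with a 7-day tolerance, then every 1-3 cycles and at progression. The section then adds "All these samples can be obtained +/- 3 days", and makes every correlative sample optional.

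On dosing, section 5.2.1 says "Lirilumab will be administered as an approximately 60 minute IV infusion on Day 8 (+/-2 days) of each 5-azacytidine cycle". Section 7.2.9 allows an interrupted azacytidine schedule at local centres: "In the event that the 5+2+2 schedule is utilized, the Lirilumab will be administered on Day 10".

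The exploratory objectives in section 1.3 concern changes in response to the two drugs given together, and the correlation of hypomethylation and DNA damage with response.

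**The concern.** A sample at the time of response exists only in patients who respond. The baseline-to-response contrast therefore conditions on the outcome, and its timing varies with when response is recorded. Most response categories in the protocol's criteria are defined by marrow blasts, so a sample taken at response also reflects a changed cell mix. A shift in a marker could be a drug effect or simply fewer blasts in the tube.

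The logistic model needs a predictor measured in responders and non-responders alike, at a time that does not depend on response. Section 11.2 does not supply one. Left open, the choice of time point can be made after the data are seen.

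The schedule already contains what is needed. The cycle 1 day 8 blood sample is the only planned on-treatment sample before any lirilumab, and no analysis names it. Its value depends on its truly being drawn before the infusion, which the general 3-day tolerance leaves unclear.

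**Working it through.** The plan gives no alpha, power, SD or sample size for the biomarker analyses, so there is no stated figure to reproduce. Two checks were made.

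**Number of pairs and detectable change.** Inputs from the plan: up to 40 phase II patients (11.1), target ORR 30% and historical ORR 10-15% (11.2). Assumptions not in the plan: two-sided alpha 0.05, power 80%, effects in SDs of the paired difference, phase II patients only.

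Responders: 40 × 0.30 = 12; 40 × 0.15 = 6; 40 × 0.10 = 4. The detectable d solves P(T > t) = 0.80, where T is noncentral t with n − 1 degrees of freedom and noncentrality d√n, and t is the 97.5% point of central t with n − 1 degrees of freedom.

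| Contrast | Pairs | Detectable d |
|---|---|---|
| Baseline to response, ORR 30% | 12 | 0.889 |
| Baseline to response, ORR 15% | 6 | 1.435 |
| Baseline to response, ORR 10% | 4 | 2.128 |
| Fixed time, all sampled | 40 | 0.454 |
| Fixed time, 70% sampled | 28 | 0.549 |
| Fixed time, 50% sampled | 20 | 0.660 |

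The first three rows assume every responder is sampled. The 70% and 50% rates are illustrations, because samples are optional. At 50% sampling the responder contrast at ORR 30% would also halve, to 6 pairs. Even against a fully sampled responder contrast, 20 fixed-time pairs detect a smaller change (0.660 against 0.889).

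Timing also varies. The first on-treatment marrow may be taken from day 28 − 7 = 21, and the primary ORR counts responses up to 3 months. With 28-day cycles, a response sample may follow one to about three cycles (91/28 = 3.25).

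**Sampling window against dosing window.** A day 8 sample with 3 days either way falls on days 5-11 (7 days). Lirilumab on day 8 with 2 days either way falls on days 6-10 (5 days). That gives 7 × 5 = 35 day pairs:

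- Sample on a later day than lirilumab: 5 + 4 + 3 + 2 + 1 = 15 (for lirilumab on days 6, 7, 8, 9, 10), by up to 11 − 6 = 5 days.
- Same day: 5.
- Sample on an earlier day: 35 − 15 − 5 = 15.

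With lirilumab on day 8, draws on days 9, 10 and 11 are within the tolerance but after the dose. With lirilumab on day 10, only day 11 is. These are counts of possible combinations, not probabilities. In the other direction, a draw on days 5-7 can precede completion of the 7-day azacytidine course. Under the interrupted schedule a day 8 draw also precedes completion; since section 7.2.9 keeps the first cycles at the trial centre, this bears mainly on later cycles. Read literally, the tolerance also reaches the baseline draw, up to 3 days into azacytidine.

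**The case against.** Several stronger conclusions are tempting, and the documents do not support them.

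- *Change is tested only at response and progression.* Section 11.2 also plans pre- against post-therapy comparisons in each patient. Their time points are unstated, so day 8 is unassigned rather than excluded. Non-responders who progress can contribute progression pairs; the plan gives no basis for counting them.
- *The logistic model cannot be fitted because non-responders lack the predictor.* The regression sentence does not tie induction to the response sample, and non-responders are scheduled for baseline, day 8 and day 21-28 blood and day 28 marrow. The fault is an undefined predictor, not an impossible model.
- *The protocol permits post-dose draws labelled as pre-dose.* Section 7.2.7 attaches the pre-dose condition to the draws themselves. A general tolerance that does not say which rule governs is an ambiguity, not a permission.
- *The objectives fail because the drugs cannot be separated.* Separation is not an objective in section 1.3. Nor would better use of day 8 achieve it: the trial is single-arm (3.0), effects of both drugs may be delayed by up to 4 weeks (5.6), and no day 8 marrow is planned.

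It is also fair to say that these are exploratory analyses of optional samples, and that the separate laboratory protocol cited in section 7.2.6, which is not available here, may contain timing detail. What survives is that the analysis section fixes time points only where the outcome sets them.

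**Conclusion.** The point holds in a limited form. The named biomarker tests are outcome-timed; the response contrast rests on about 12 patients at the target ORR and 4-6 at the historical rate; and fixed-time samples that could give up to 40 pairs are not named in any analysis. Under the assumed alpha and power, the detectable change falls from 0.89 SD to 0.45 SD with full sampling. These contrasts answer different questions and their SDs may differ, so the figures illustrate information lost rather than an exact gain. The gain shrinks with incomplete sampling and early drop-out.

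The window and the pre-dose condition need reconciling; how often they would clash in practice is unknown. The exploratory objectives are weakened rather than unanswerable. Nothing here touches the primary endpoint, the safety analysis or the stopping rules.

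**What to change.** In section 11.2:

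- Make the main biomarker contrasts fixed-time in all sampled patients. In blood, use baseline to cycle 1 day 8 before lirilumab, and day 8 to days 21-28. In marrow, use baseline to day 28.
- Describe day 8 to days 21-28 as change after lirilumab is added to azacytidine, not as a lirilumab effect.
- Define the logistic predictor as a fixed early change, for example baseline to day 8 in blood.
- Keep the response- and progression-time contrasts as descriptive.

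In section 7.2.7:

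- State that the pre-dose condition overrides the 3-day tolerance, so the day 8 sample is drawn before lirilumab and, where possible, after the last azacytidine dose. A blanket allowance of up to 3 days early would not do, because it would let the draw fall mid-course.
- Record draw and dose dates and times, and analyse any post-dose draw as post-dose.

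The cost is wording and recorded times, with no new samples. A few late draws would leave the pre-dose set.
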